7.4 Handling of adverse events

- Reporting method

Any adverse events, such as patients' subjective discomfort and abnormal laboratory tests, should be taken seriously and analyzed carefully. Any adverse events, such as subjective discomfort of the patient and abnormal laboratory tests, should be taken seriously, analyzed carefully, and immediate measures should be taken to protect the safety of the subjects.

- Handling procedure

Record in detail in CRF, and record its persistence, regression and disappearance as appropriate.

- Handling of serious adverse events

If any serious adverse event occurs, the investigator should not only give prompt treatment on site, but also report to the clinical trial unit in charge and the investigator within 24 hours. Within 24 hours, the investigator should report to the unit in charge of the clinical trial and the monitor of the clinical trial; and within 24 hours, the investigator should report in writing to the State Food and Drug Administration (SFDA). Within 24 hours, the investigator shall report in writing to the State Food and Drug Administration on the occurrence of the adverse event and its handling.

Treatment: When a patient has an emergency situation, the principal investigator of the study unit will do the appropriate treatment according to the drug and the symptoms presented, notify the clinical supervisor of the results of the treatment, and the investigator should record the treatment in detail, the results, and sign on the case report form.

- Follow-up of unrelieved adverse events

All adverse events should be followed up until properly resolved or stabilized. All adverse events with predominantly test values should be followed up with laboratory results until normal

8 Data management

The investigator loaded the data into the case report form in a timely, complete, correct, and legible manner based on the subjects' original observation records.

Supervisors monitored that the study was conducted in accordance with the study protocol. Confirm that all case report forms were completed correctly and consistent with the original data. In case of errors and omissions, the researcher was asked to make corrections in a timely manner. Corrections should be made in such a way that the original record is legible and the corrections should be signed and dated by the investigator.

After checking by the supervisor, the case report form will be verified and signed by the supervisor, and then sent to the Clinical Research Data Manager in a timely manner.

There should be a special record of the transmission of the completed case report form between the investigator, the supervisor and the data manager, with appropriate signatures on receipt, and the record should be kept appropriately.

The data manager will check the data again before data entry and notify the supervisor of any problems and ask the investigator to answer them. The exchange of questions and answers between them should be in the form of a questionnaire, which should be kept for reference.

The data manager should understand the content and coding of each item of the observation form before data entry, and record the coding work process in the coding book for preservation. Database naming should be standardized, easy to read and easy to find. And ensure its correctness, security and confidentiality.

The data entry clerk enters the data using secondary entry. Problems or unforeseen circumstances found during the entry process should be registered and reported in time so that the problems can be dealt with quickly. After the data entry is finished, some of the observation forms should be sampled to understand the quality of entry, and to analyze and deal with the existing problems.

The data manager should work together with the principal investigator to formulate the content of data range checking and logic checking according to the ranges and interrelationships of the values of each indicator in the case report form. The corresponding computer program should be prepared to control erroneous data entry before input, to find out the causes of errors and to correct them, and all the contents of errors and the results of modification should be recorded and properly preserved.

After completing data entry and verification as required, the original case report form should be filed and stored in the order of numbering and filled with a retrieval catalog, etc., to The original case report form should be filed and stored in a numbered order and filled with a search catalog for reference. Electronic data files include databases, examination procedures, analytical procedures,

analysis results, codebooks and description documents, etc., should be classified and stored with multiple backups on different disks or recording media for proper preservation. The electronic data files, including databases, inspection procedures, analytical procedures, analytical results, codebooks, and description files, should be kept in categories with multiple backups on different disks or recording media.

Appendix I.

Symptom-based assessment of anorexia

Please circle the answer you think is correct for each entry in the questionnaire below.

Entry	None	+	++	+++	++++
Good appetite	 0	 1	 2	 3	 4
Adequate food intake	 0	 1	 2	 3	 4
Worried about being	 0	 1	 2	 3	 4

overweight					
Most foods do not taste good to me	 4	 3	 2	 1	 0
Worried about losing weight	 4	 3	 2	 1	 0
Lack of interest in food when eating	 4	 3	 2	 1	 0
Difficult to eat rich or large amount of food	 4	 3	 2	 1	 0
Urged to eat by family and friends	 4	 3	 2	 1	 0
Vomiting	 4	 3	 2	 1	 0
Early satiety	 4	 3	 2	 1	 0
Pain in stomach and wrist	 4	 3	 2	 1	 0
Improving health	 0	 1	 2	 3	 4

Total Score

After the patient answered all the questions in the table, the score was evaluated, and the final score ≤ 24 points, it can be recognized as anorexia nervosa.

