
This research proposal is in response to the National Natural Science Foundation of China's top-level project (Project No. 81573958; Title:

Auricular Acupuncture for Clinically Advanced Tumor Patients' Appetite Intervention and Mechanism Research).

Research Objectives

To objectively evaluate the clinical efficacy of auricular acupuncture in improving the appetite of tumor patients, to verify and improve its technique, to determine the therapeutic points and treatment course, and to provide a strong evidence-based medical basis for auricular acupuncture intervention in tumor therapy. We will validate and improve its technique, determine the therapeutic points and treatment course, and provide a strong evidence-based

medical basis for the intervention of auricular acupuncture in the treatment of tumors.

Research content

1 Type of study design

This study used a randomized, parallel-controlled research method. Based on the principle of voluntary participation, baseline information was included and collected, random seeds were generated by the SAS 9.2 statistical software random seed generator, and in a ratio of 1:1, it was proposed to randomly assign 60 subjects meeting the inclusion criteria to the ear acupuncture group and the control group. Each group of 30 cases, statistical expert design, after the preparation of the randomization scheme, the control and implementation of the allocation by those who are not directly involved in the grouping.

2 Sample size setting

This study was an exploratory study, considering 30 cases in each group, totaling 60 patients.

3 Study population

Sixty patients with anorexia nervosa of malignant tumors of stage III and IV who attended outpatient clinics or were hospitalized in the Department of Oncology of Xiyuan Hospital of China Academy of Traditional Chinese Medicine from May 1, 2016 to October 31, 2017.

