3.1 Diagnostic criteria

3.1.1 Western medical diagnostic criteria

There is no uniform diagnostic standard for anorexia nervosa. Referring to the "Diagnostic and therapeutic pathway of anorexia nervosa" of the Professional Committee of Tumor Nutrition and Supportive Therapy of the Chinese Anti-cancer Association, based on the "Symptom-based assessment table", we shall evaluate whether anorexia nervosa occurs in the patients who are clearly diagnosed with tumors and the degree of its occurrence. The patient is asked to answer all the questions in the scale. After the patients answered all the questions in the scale, the scores were evaluated, and the final score ≤ 24 points could be recognized as anorexia.

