6.2 Diagnostic indicators

Tumor pathology, staging, symptom-based anorexia assessment, TCM evidence.

6.3 Main observational indexes: refer to the "Anorexia Diagnosis and Treatment Pathway" of the Professional Committee of Tumor Nutrition and Supportive Therapy of the Chinese Anti-Cancer Association.

① Symptom-based anorexia evaluation form: Appendix I.

② Simplified Appetite Scale: Appendix V.

6.4 Secondary observation indicators:

① Fatigue Symptoms Scale: Appendix III.

② Patient's expectation of acupuncture: Appendix II. Appendix II

Appetite level: VAS is a semi-quantitative assessment of the degree of anorexia nervosa.

Drawing on the practice of foreign countries in the last century and the idea of VAS assessment for cancer pain in China, it is suggested that a 10 cm long travel scale with 10 scales on one side and "0" and "10" marks on the other side should be used. The scale has 10 marks on one side, with the "0" and "10" markings on both ends, with the "0" marking indicating a normal appetite and the "10" marking indicating an extreme aversion to food. When using the graduated side of the back to the patient, let the patient in the ruler marked on the degree of their desire for food on the corresponding position, the physician according to the position marked by the patient for its score, clinical evaluation to "0-2" is "normal appetite / basic normal eaters The clinical assessment is "0-2" as "normal appetite/basic normal eater", "3-5" as "mild anorexia", "6-8" as "moderate anorexia", and >8 as "anorexia". The score of "3-5" was classified as "mild anorexia", "6-8" as "moderate anorexia", and ">8" as "severe anorexia". The efficacy of the treatment was evaluated according to the change in appetite. Effective: improvement level greater than or equal to 1; stable: no change in level; ineffective: decrease in level.

④ Weight. Weight changes caused by factors other than fluid accumulation in the body cavity and swelling. Improvement: weight gain >2Kg and maintained for more than 4 weeks. Stable: weight gain or loss of ≤ 2 Kg. deterioration: weight loss of >2Kg. 5.

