### 2 Statistical analysis plan

Statistical analyses will be calculated using SAS 9.2 statistical analysis software.

The primary validity analysis dataset will be FAS, and PPS will also be analyzed.

All statistical tests will be two-sided, and a p-value of less than or equal to 0.05 will be considered a statistically

The differences tested were considered statistically significant.

Measures for each visit in the different treatment groups were described statistically as mean  $\pm$  standard deviation. Comparisons were made with the baseline values at the time of enrollment using the paired t-test. The paired t-test was used to compare pre- and post-treatment differences within groups. Changes before and after treatment in each group were compared using analysis of variance (ANOVA). The count data of each visit of different treatment groups were statistically described by frequency counts (constitutive ratio). Changes before and after treatment in each group were analyzed using the  $\chi^2$  test or nonparametric The  $\chi^2$  test or non-parametric test was used.

Shedding analysis: The  $\chi^2$  test will be used to compare the total shedding rate and the shedding due to adverse events in each group.

Balanced analysis of baseline values: ANOVA or  $\chi^2$  test will be used to compare demographic data and other baseline indicators to measure how well balanced the two groups are. measure how well the two groups are balanced.

Effectiveness analysis: PPS and FAS were used to analyze the primary and secondary indicators; since this study is a multicenter clinical trial, the impact of central effects on the efficacy indicators should be considered in the analysis. Since this study is a multicenter clinical trial, the influence of center effect on the efficacy indexes should be considered in the analysis.

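### Item 3 of the Appendix I anorexia form, worry about being overweight, is scored in the opposite direction to every other worry or symptom item, so its wording and key need checking before scoring

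*Protocol*

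**What the plan says.** Appendix I of the Protocol prints a twelve-item form with five answer levels from None to ++++. Item 1, "Good appetite", and the items on food intake and improving health score 0 for None up to 4 for ++++. Item 3 has the same key. Its label is split across two lines: "Worried about being" and then overweight. The split affects the label only; the printed scores are intact. Item 5, "Worried about losing weight", and the seven items on taste, interest in food, difficulty eating, being urged to eat, vomiting, satiety and pain score 4 for None down to 0 for ++++.

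The total has two uses. Protocol section 3.1.1 uses it for diagnosis: "the final score ≤ 24 points could be recognized as anorexia". Appendix I repeats the cut-off. Section 6.3 lists the form first of the two main observational indexes: "Symptom-based anorexia evaluation form: Appendix I". Sections 6.5.2 and 6.5.3 collect it at weeks 2, 4 and 8. The statistical analysis section of the SAP gives no item-scoring rule, so the printed key is the one an analyst would apply.

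**The concern.** Since low totals mean anorexia, a high item score should mark a better state. The three other items keyed upwards name desirable states, and the eight items keyed downwards name worries or symptoms. Item 3 names a worry but is keyed like a desirable state.

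Two things follow if the form is used as printed. A patient who eats well and has no worry about weight in either direction gets the lowest possible score on item 3. The only way to gain points on it is to become more worried about being overweight, whereas the Protocol's stated objective is better appetite. A general worry about weight would also move items 3 and 5 in opposite directions.

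The total decides who counts as anorexic and is a main outcome, so a fault in one item can touch both uses.

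**Working it through.** **Inputs.** From Appendix I: twelve items scored 0 to 4; items 1, 2, 3 and 12 ascend and items 4 to 11 descend. From section 3.1.1 and Appendix I: anorexia is a total ≤ 24. The plan has no figure to reproduce here: there is no scoring manual, and the sample size ("This study was an exploratory study, considering 30 cases in each group, totaling 60 patients") comes without an effect size, standard deviation or power.

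**Range.** 12 × 4 = 48, so totals run from 0 to 48 under either key, and 24 is the midpoint.

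**Ceiling.** Best answers on the other eleven items give 11 × 4 = 44. With no worry about overweight the printed total is 44 + 0 = 44. With the greatest worry it is 44 + 4 = 48. Under a reversed key these become 48 and 44.

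**Difference between keys.** Let x be the answer to item 3 (None = 0 to ++++ = 4). The printed score is x and the reversed score is 4 − x. Reversed minus printed is 4 − 2x.

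**Change of diagnosis.** Let S be the sum of the other eleven items. The printed key gives anorexia if S + x ≤ 24, that is S ≤ 24 − x. The reversed key gives it if S + 4 − x ≤ 24, that is S ≤ 20 + x.

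| Answer | x | 4 − 2x | Printed: S ≤ | Reversed: S ≤ | S at which status changes |
|---|---|---|---|---|---|
| None | 0 | +4 | 24 | 20 | 21 to 24 |
| + | 1 | +2 | 23 | 21 | 22 to 23 |
| ++ | 2 | 0 | 22 | 22 | none |
| +++ | 3 | −2 | 21 | 23 | 22 to 23 |
| ++++ | 4 | −4 | 20 | 24 | 21 to 24 |

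For None and +, the patient is anorexic as printed and not anorexic if reversed. For +++ and ++++ it is the other way round. For example, with the answer None and S from 21 to 24, the printed totals are 21 to 24 and the reversed totals are 25 to 28.

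**Outcome.** Let D11 be the between-arm difference in mean change on the other eleven items, and D3 the same difference in the answer to item 3. The printed total gives D11 + D3 and the reversed total gives D11 − D3; they differ by 2 × D3. If D3 = 0 the two keys give the same mean difference. If each patient's answer to item 3 stays the same, it cancels from that patient's change and adds no variance to it. If answers move, the key alters how item 3 combines with the other items, and this is where noise or dilution could enter. The documents give no data on D3.

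**The case against.** The strongest reply is that nobody can call this an error without the source form. The Protocol takes the form from a cited pathway and gives no item rationale, so a wrong key, a mistranslated label and a deliberate key all remain possible. Mistranslation is credible: the pain item mentions the wrist, and the performance score appears under several spellings. In patients who under-eat, items 3 and 5 might also be meant as opposite poles, which would explain opposite keys.

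Much of this stands. A reader might infer that the key is proven wrong and distorts the results; the documents do not establish that. A reader might also infer that item 3 removes a fixed share of the treatment effect. An item that does not respond contributes nothing under either key. A loss through opposition needs overweight worry to fall as the other items improve, and a patient already at None cannot fall further. Nor do the documents show that the entry threshold is shifted: if ≤ 24 was set on this form as printed, the cut-off already allows for item 3, and reversing the item would detach the cut-off from its form.

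The opposite-poles reading does not remove the point. It does not explain why having neither worry should earn the worst score on item 3.

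**Conclusion.** The inconsistency is real and its extent is bounded. Item 3's wording and key do not fit together in the way the rest of the form does, and the documents do not show which of the two is at fault. The most that one patient's total can move is 4 of 48 points. Diagnosis is at risk only in the narrow bands tabulated above, and only if the cut-off was set on a differently keyed form.

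For the outcome, the risk is noise or dilution. A reader might suspect bias toward one arm, but the same key applies to both arms and nothing in the documents points that way. How patients answer item 3, and whether those answers change, is not known from the documents, so no loss of effect or power can be stated. The point still merits action because it concerns a main outcome and is cheap to settle before scoring.

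**What to change.** Before any scoring, compare item 3's wording and key with the source form in the cited pathway, and confirm on which version of the form ≤ 24 was set. Record the result and the scoring rule in the SAP. The coding book that Protocol section 8 already requires is a natural place to document the check.

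- If the wording is wrong, correct the label and keep the key.
- If the key is wrong, score item 3 as 4-3-2-1-0 and recompute every baseline and follow-up total, and the ≤ 24 status, from item-level answers. Keep all randomised patients in the FAS, including any whose baseline status changes.
- If the source confirms both, keep the form and state why the item is keyed this way.

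In every case, report the 11-item total without item 3 as a sensitivity analysis of the outcome. Its range is 0 to 44, and the ≤ 24 cut-off does not carry over to it.

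The cost is one check of the form, rescoring if needed, and one extra analysis. Rescoring depends on item-level answers being kept; sections 6.5.2 and 6.5.3 name the form but do not say so, and the data management plan should.

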Appendix II

Acupuncture Expectations Questionnaire

Every patient has different expectations about the efficacy of acupuncture. If you were to use the following sentences to describe how you feel about your disease/symptoms after a full course of acupuncture, how much would you agree? Please select the closest answer for each question.

	Totally disagree	Somewhat agree	Comparatively agree	Generally agree	Totally agree
a. I will get much better					
b. I can cope with my illness better					
c. the symptoms of my illness will go away					
d. I will have more energy than before					

Appendix III

Fatigue Symptom Inventory(FSI)

This questionnaire is designed to find out your level of fatigue during treatment. Please circle the number that best describes your condition according to the following questions!

1. Please evaluate the extent to which you have felt most tired in the last 7 days.

0 1 2 3 4 5 6 7 8 9 10

Not at all

I can feel

No fatigue

Maximum fatigue

2. Please rate the least tired you have felt in the last 7 days?

0 1 2 3 4 5 6 7 8 9 10

Not at all

I can feel

No fatigue

Maximum fatigue

3. Please evaluate the average level of fatigue you have experienced in the last 7 days?

0 1 2 3 4 5 6 7 8 9 10

Not at all

I can feel

No fatigue

Maximum fatigue

4. Please rate your current level of fatigue?

0 1 2 3 4 5 6 7 8 9 10

Not at all

I can feel

No fatigue

Maximum fatigue

5. Please assess to what extent fatigue has affected your general activities in the last 7 days?

0 1 2 3 4 5 6 7 8 9 10

No effect

Extreme effect

6. Please assess how much fatigue has affected your ability to bathe and dress yourself in the last 7 days?

0 1 2 3 4 5 6 7 8 9 10

No effect

Extreme effect

7. Please assess how fatigue has affected your normal work activities (both outside work and at home) in the last 7 days.

0 1 2 3 4 5 6 7 8 9 10

No effect

Extreme effect

8. Please assess how fatigue has affected your ability to concentrate in the last 7 days.

0 1 2 3 4 5 6 7 8 9 10

No effect

Extreme effect

9. Please assess how fatigue has affected your relationships with others in the last 7 days?

0 1 2 3 4 5 6 7 8 9 10

No effect

Extreme effect

10. Please assess how much fatigue has affected your enjoyment of life in the last 7 days?

0 1 2 3 4 5 6 7 8 9 10

No effect

Extreme effect

11. Please assess how much fatigue has affected your mood in the last 7 days.

0 1 2 3 4 5 6 7 8 9 10

No effect

Extreme effect

12. On how many of the last 7 days did you feel tired at any given moment?

0 1 2 3 4 5 6 7

Days

Days

13. In the question above, how tired did you feel on average during the day?

0 1 2 3 4 5 6 7 8 9 10

No fatigue

Feeling fatigued all day

14. In the last 7 days, which best describes your daily state of fatigue?

0 1

1

2

3

4

Not at all

Morning m

Afternoon

st Evening

ost Tired every day

The questionnaire is divided into three parts, with questions 1-4 measuring the intensity of fatigue, including most fatigued, least fatigued, average fatigue, and currently fatigued; questions 5-11 measuring the extent to which fatigue interferes with quality of life; and questions 12-13 measuring the duration of fatigue (durations of fatigue). The questions measured the duration of fatigue, including the number of days fatigue occurs, the time of day; the scoring method, except for question 12, which measured the number of days fatigue occurs with 0-7, the other questions were 0-10 to indicate the presentation of symptoms of fatigue, with 0 representing no fatigue at all, and 10 representing the maximum amount of fatigue I can feel. 0 means no fatigue at all, and 10 means I can feel maximum fatigue. Only questions 5-11 can be summed up to represent the degree of interference with life, with a total score of 70 points; the higher the score, the higher the degree of interference of fatigue with life, and the other questions are scored individually to represent the degree of interference with the topic, with a total of 10 points for each question.

